3 STUDY DESIGN

This study will be a prospective study, with 50 subjects total, who are between ages 18 and 49 years of age, in good health and meet all eligibility criteria. Each subject will make a total of 7 visits to the Hope Clinic. Subjects will be recruited from the Atlanta metro area. (See appendix). 30 of the subjects will also have two different visits at the GI suite during which small intestinal biopsies will be obtained: one at screening (-45 to -7 days) and the other post vaccination (Group 1 at Day 29 -7 days/ +14 days and Group 2 at day 90 +14 days) by EGD, and will have an additional follow-up phone call 7 days after the procedure. Subjects will be recruited from the Atlanta metro area.

4 STUDY POPULATION

4.1 Selection of the Study Population

The target sample size will be 50 subjects who will receive the Vaxchora live cholera vaccine, of whom 30 will undergo two procedures for small intestinal biopsies (6-12 biopsies per EGD procedure in total): one at screening and the other post vaccination (Group 1 at Day 29 and Group 2 at day 90) by an EGD. With the exception of the inclusion/exclusion criteria, there will be no intentional recruitment of particular ethnic or racial groups. Subjects will be screened for eligibility according to the inclusion/exclusion criteria by history. Informed consent will be obtained for study participation.

4.2 Inclusion/Exclusion Criteria

Subjects eligible to participate shall meet all of the following **inclusion criteria**:

1. Capable of informed consent and provision of written informed consent before any study procedures.
2. Capable of attending all study visits according to the study schedule.
3. Males or females between the ages of 18 and 49 years of age (inclusive).
4. Are in good health, as determined by medical history and targeted physical exam related to this history.
5. Female subjects of childbearing* age must have a negative urine pregnancy test before study vaccination and must use two forms of contraception** to avoid pregnancy within one month of Vaxchora administration.

** Not sterilized via tubal ligation, bilateral oophorectomy, hysterectomy, or successful Essure® placement (permanent, non-surgical, non-hormonal sterilization) with documented radiological confirmation test at least 90 days after the procedure, and still menstruating or <1 year of the last menses if menopausal..*

***Includes, but is not limited to, non-male sexual relationships, abstinence from sexual intercourse with a male partner, monogamous relationship with vasectomized partner who has been vasectomized for 180 days or more prior to the subject receiving the first study vaccination, barrier methods such as condoms or diaphragms with spermicide or foam, effective intrauterine devices, NuvaRing®, and licensed hormonal methods such as implants, injectables, or oral contraceptives ("the pill").*

Subjects eligible to participate shall not meet any of the following **exclusion criteria**:

1. Have an acute illness within 72 hours before vaccination.

-
2. Have any acute or chronic medical condition that, in the opinion of the principal investigator, would make vaccination unsafe or interfere with the evaluation of immune response to study vaccination.
 3. Have a suppressed immune system as a result of illness, immunosuppressive medication, chemotherapy, or radiation therapy within 3 years prior to study vaccination.
 4. Have taken oral or parenteral corticosteroids of any dose within 30 days before study vaccination.
 5. Reside with individuals under the age of 2 or with an immunocompromised individuals.
 6. Have a known history of autoimmune disease.
 7. Have a history of Guillain-Barre Syndrome.
 8. Have plans to receive any vaccine from 28 days prior to study vaccination until Day 29.
 9. Has previously received a cholera vaccine or have a known history of *V. Cholerae*.
 10. Have donated blood or blood products within 56 days before study vaccination, plan to donate blood at any time during the 56-day duration of subject study participation, or plan to donate blood within 56 days after the last blood draw.
 11. Have known hypersensitivity or allergy to any component of the vaccine or history of anaphylaxis with a vaccine or vaccine component.
 12. Have allergy to tetracycline and/or ciprofloxacin.
 13. Are pregnant or breastfeeding or plan to within one month of vaccination.
 14. Travelled to a cholera endemic area and had traveler's diarrhea in the previous 5 years.
 15. Have abnormal stool pattern (fewer than 3 stools/ week or greater than 2 stools/ day) or regular use of laxatives in the last 6 months.
 16. Have current or recent antibiotic use in the past 14 days.
 17. Are healthcare workers who have direct contact with patients who are immunocompromised, have unstable medical conditions, or are under the age of 2.
 18. Are childcare caregivers who have direct contact with children who are 2 years or younger.
 19. Are employed in the food industry.
 20. Have received any vaccine within the previous 21 days.
 21. History of bleeding disorders or current use of warfarin, aspirin, heparin, nonsteroidal anti-inflammatory drugs (NSAIDs) or other blood thinner/ anticoagulant medications in the past week for subjects undergoing intestinal biopsies.
 22. Use of benzodiazepines or narcotics for subjects undergoing intestinal biopsies 4 weeks prior to the procedure
-

-
23. Any contraindications to endoscopy/concerns of the anesthesiologist for subjects who agree for EGD/biopsies.
 24. BMI > 35 kg/m²
 25. Have a diagnosis of any small bowel disease. This includes but is not limited to inflammatory bowel disease (e.g., Crohn's disease, ulcerative colitis, indeterminate colitis, or microscopic colitis), small bowel obstruction, celiac disease, h/o small bowel resection, small bowel lymphoma, Whipple's disease, primary Intestinal lymphangiectasis, abdominal radiation.
 26. Current medications for the treatment of Gastroesophageal reflux disease (GERD) or dyspepsia
 27. History of Helicobacter pylori (H. pylori) infection

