2.2 Study Outcome Measures

Primary:

- Level of antibody titers at day 1 (pre-vaccination) and day 29 in serum.

Secondary:

- Levels of plasmablasts at days 1, 8 and 29
- Levels of activated B cells at days 1, 8 and 29
- Levels of memory B cells at days 1 and 29 .
- Correlation between antibody titers and the level of plasmablasts, activated B cells, and memory B cells.
- Production and characterization of monoclonal antibodies at day 8 against *V. cholerae* in a subset of subjects.
- Solicited and unsolicited adverse events in healthy subjects receiving cholera vaccine at day 8 and day 29 respectively.

- Serious adverse events in healthy subjects receiving cholera vaccine for the duration of the study

Exploratory:

- Levels of plasmacells, activated B cells and T cells in small intestinal biopsy samples at day 29 (n=15) or day 90 (n=5).
- Correlation between systemic and mucosal immune responses.
- Production and characterization of monoclonal antibodies against *V. cholerae* from a protected mucosal site.
- Levels of antibody titers at days 90 and 365.
- Levels of plasmablasts at days 11 and 15 in a subset of subjects.
- Levels of activated B cells at days 11 and 15 in a subset of subjects.
- Levels of T cells at days 1 and 29 in a subset of subjects.

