6 STUDY SCHEDULE

6.1 Screening and Enrollment/Baseline Visit

6.1.1 Screening Visit Day 00 (As needed) (Day -45 to -7 days)

Study subjects will be given a description of the study and have an opportunity to have their questions and concerns addressed by the study principal investigator or designee.

Subjects will be given the informed consent form to read and discuss with study staff, and if they wish to enroll will sign the document before any study vaccination, procedures, or lab draws are performed.

A medical history and targeted physical exam, if necessary, as outlined in the Study Procedures section will be conducted in order to assess for compliance with study inclusion and exclusion criteria.

A list of any medications taken by subjects in the past 30 days and those to be taken for 28 days after vaccinations will be documented on the appropriate study form.

A urine pregnancy test will be conducted for female subjects, and a negative result will be required and be documented on the appropriate study form prior to any study interventions.

Vital signs, including pulse rate, blood pressure, oral temperature, and height and weight will be measured and documented on the appropriate study form.

Group 1 and Group 2 subjects: a procedure for small intestinal biopsies using esophagogastroduodenoscopy will be performed by a gastrointestinal specialist at Emory GI suite. Visit will take 4 hours.

6.1.2 Visit 0a (screening+7) for groups 1 and 2

Groups 1 and 2: a follow-up phone call is made 7 days post procedure to assess for any adverse events from the EGD procedure.

6.1.3 Enrollment Day 01

Study subjects will be given a description of the study and have an opportunity to have their questions and concerns addressed by the study principal investigator or designee.

Subjects will be given the informed consent form to read and discuss with study staff (if no screening visit has been done), and if they wish to enroll will sign the document before any study vaccination, procedures, or lab draws are performed.

A medical history and targeted physical exam, if necessary, as outlined in the Study Procedures section will be conducted in order to assess for compliance with study inclusion and exclusion criteria.

A list of any medications taken by subjects in the past 30 days and those to be taken for 28 days after vaccinations will be documented on the appropriate study form.

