6.2 Follow-up and Final Visits

6.2.1 Visit 02 Day 08 Visit 03 Day 11, Visit 04 Day 15

Interim medical history and targeted physical exam, if necessary, will be conducted.

Medications taken during the interim from the previous visit and any adverse or serious adverse events will be documented on the appropriate study form.

Vital signs, including pulse rate, blood pressure, and oral temperature will be measured and documented on the appropriate study form-

Blood will be collected for immunogenicity analysis.

A review of the memory aid will be done at Visit 02.

Certain follow up visits (D11 and D15) will not be required by PI discretion.

6.2.2 Visit 05 Day 29

Interim medical history and targeted physical exam, if necessary, will be conducted.

Medications taken during the interim from the previous visit and any adverse or serious adverse events will be documented on the appropriate study form.

Vital signs, including pulse rate, blood pressure, and oral temperature will be measured and documented on the appropriate study form.

Blood will be collected for immunogenicity analysis.

Group 1 (n=15): a small intestinal biopsy using esophagogastroduodenoscopy will be performed by a gastrointestinal specialist at Emory GI suite. Visit will take 4 hours. The window for this visit is – 7 days/ + 14 days

6.2.3 Visit 06 Day 90

Interim medical history and targeted physical exam, if necessary, will be conducted.

Any serious adverse event will be documented on the appropriate study form.

Vital signs, including pulse rate, blood pressure, and oral temperature will be measured and documented on the appropriate study form-

Blood will be collected for immunogenicity analysis

Group 2 (n=5): a small intestinal biopsy using esophagogastroduodenoscopy will be performed by a gastrointestinal specialist at Emory GI suite. Visit will take 4 hours. The window for this visit is + 14 days. Visit 05a (EGD +7 days) and Visit 06a (EGD day+7 days)

Group 1 and 2: a follow-up phone call is to be made 7 days post-procedure to assess for any adverse events from the procedure. Visit 07 Day 365

Interim medical history and targeted physical exam, if necessary, will be conducted.

Any serious adverse event will be documented on the appropriate study form.

Vital signs, including pulse rate, blood pressure, and oral temperature will be measured and documented on the appropriate study form.

Blood will be collected for immunogenicity analysis

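### The bar on other planned vaccines stops at Day 29, but the Day 29 visit may run to Day 43, so the cell counts of subjects seen late could include another vaccine's response

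*Combined protocol and SAP*

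**What the plan says.** Exclusion 8 in Section 4.2 applies to subjects who "Have plans to receive any vaccine from 28 days prior to study vaccination until Day 29". It names a day, not a visit or a sample, and it screens intentions at entry. Exclusion 20 also concerns other vaccines but looks only backward from enrolment.

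The timing of the visit is given in three places. Section 3 schedules the post-vaccination biopsy as "Group 1 at Day 29 -7 days/ +14 days and Group 2 at day 90 +14 days". Section 6.2.2 says, directly after describing the Group 1 biopsy, "The window for this visit is – 7 days/ + 14 days". The Appendix A schedule puts the same -7/+14 window on the whole of Visit 05, including the venous blood collection.

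That visit supplies the second primary measurement ("Level of antibody titers at day 1 (pre-vaccination) and day 29 in serum") and the last time point of two secondary cell endpoints ("Levels of plasmablasts at days 1, 8 and 29" and "Levels of activated B cells at days 1, 8 and 29"). It also supplies the Day 29 memory B cell and T cell samples and the Group 1 biopsy counts. Section 2.2 does not say whether the plasmablast, activated B cell or biopsy cell counts are restricted to cholera-specific cells.

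On concomitant products, Section 6.1.1 says that medications taken in the previous 30 days and "those to be taken for 28 days after vaccinations will be documented on the appropriate study form". Section 6.2.2 and Appendix A record medications at Visit 05, and Section 5.1 counts vaccines within the pre-vaccination medication history. Section 7 plans descriptive statistics and has no rule for a sample taken after another vaccine.

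**The concern.** The bar on other vaccines presumably exists so that the Day 29 measurements reflect Vaxchora alone. It does that only if it lasts until the samples are taken. For a subject seen after Day 29 it may already have ended, and that subject can receive an unrelated vaccine and be sampled afterwards without departing from the protocol.

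Every subject receives Vaxchora, so no control group would reveal a response that came from something else. A raised plasmablast or activated B cell level at Visit 05 would naturally be read as persistence of the cholera response. It would also enter the planned correlations with antibody titers and between systemic and mucosal responses.

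**Working it through.** The protocol gives no figure on this point to reproduce, so the check is date arithmetic followed by an illustrative range.

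**1. Visit window (Appendix A).** Earliest day: 29 - 7 = 22. Latest day: 29 + 14 = 43. Permitted days: 43 - 22 + 1 = 22.

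**2. Length of the gap.** The bar ends on Day 29 (exclusion 8), so it can lapse up to 43 - 29 = 14 days before sampling. The uncovered days are 30 to 43, which is 14 of the 22 permitted days (14/22 = 64%). If Day 29 itself is barred, the earliest free day is Day 30, which is 43 - 30 = 13 days before the latest possible draw.

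**3. The 7-day time point.** The study samples its own plasmablast and activated B cell response on Day 8, which is 8 - 1 = 7 days after vaccination. The same lag applied to another vaccine gives 30 + 7 = 37 and 36 + 7 = 43. A vaccine on Days 30 to 36 therefore has its 7-day point on Days 37 to 43. Those are 7 of the 22 permitted days (7/22 = 32%).

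**4. Calendar day or visit?**
- Section 3 uses Day 29 as the anchor from which the window runs.
- Section 6.3 uses D29 as a cut-off for recording medications and adverse events.
- The medication period in Section 6.1.1 ends on calendar Day 1 + 28 = 29.
- Against these, Section 6.2.2 heads the visit itself as Day 29.

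The balance favours a calendar day, but the text does not settle it.

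**5. Weight of one subject.** One affected subject is 1/50 = 2% of the sample. In Group 1 it is 1/15 = 7% or 1/25 = 4%, because Section 6.2.2 gives 15 and the Appendix A footnote gives 25.

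**6. Chance of at least one affected subject.** The protocol gives no uptake of other vaccines. Assume that a share p of subjects receives one in the gap before Visit 05. The chance of at least one among n is 1 - (1 - p)^n.

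| Assumed p | n = 50 (expected number) | Group 1, n = 15 | Group 1, n = 25 |
|---|---|---|---|
| 1% | 39% (0.5) | 14% | 22% |
| 5% | 92% (2.5) | 54% | 72% |
| 10% | 99% (5) | 79% | 93% |

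These rows illustrate assumptions and are not estimates. The true p also requires that the subject is seen after Day 29.

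**The case against.** The strongest reply is that Day 29 is used as a visit label. Section 6.2.2 is headed that way, and outcomes described as Day 29 are collected at the windowed visit. If exclusion 8 means the visit, there is no gap. This reading is possible, and in that case the edit below only makes the intention explicit.

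Five further points carry weight:

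- **Primary endpoint.** Because the primary titer is drawn at Visit 05, a reader might infer that it is biased. The documents do not support that. The primary objective concerns the antibody response to the cholera vaccine, and nothing shows that an unrelated vaccine would move a cholera-specific titer.
- **Cell endpoints.** The harm needs total counts. If the assays are antigen-specific, most of the concern falls away. The Day 8 measurements are untouched either way.
- **Biopsies.** Nothing in the documents shows that a vaccine given elsewhere in the body changes cell counts in the small intestine. This part is the least certain.
- **Window for the blood draw.** Sections 3 and 6.2.2 attach the -7/+14 window to the Group 1 biopsy. For subjects without that biopsy it rests on the Appendix A column header alone.
- **Recording.** Medications are already documented at Visit 05, so another vaccine might well be captured. What is missing is an explicit instruction to record it and a rule for the affected sample.

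A reader might also take 64% as the chance that a subject is exposed. It is a share of permitted days. Visits aim at Day 29, and the 7-day scenario needs both a late visit and a vaccine in a particular week.

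On the other side, the scenario is not far-fetched. Section 5.0 recruits through vaccine-centre mailing lists and among current clinic subjects, and no exclusion bars taking part in another study.

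**Conclusion.** The mismatch is real on the calendar reading: the bar can end up to 14 days before the Visit 05 samples, and no other section bars a vaccine in that interval or says how to handle the sample. At stake are the Day 29 plasmablast and activated B cell levels, which are secondary, and less certainly the exploratory Group 1 biopsy counts and the correlations that use either. This conclusion rests on three assumptions: Day 29 is a calendar day, the counts are total rather than cholera-specific, and some subjects seen late receive another vaccine first. The number affected cannot be derived from the documents and is probably small. This is a cheap improvement to a descriptive, uncontrolled study, not a flaw that undermines it.

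**What to change.** 1. In exclusion 8, tie the end of the period to completion of the Visit 05 sampling, including the biopsy for Group 1. Wording it as Day 29 or completion of that sampling, whichever is later, avoids shortening the present bar for subjects seen before Day 29.
2. Exclusion 8 screens plans only, so rewording it cannot stop an unplanned vaccine. Use the existing Visit 05 medication review to record the date and type of any other vaccine received since Day 1.
3. In Section 7, prespecify a sensitivity analysis of the Visit 05 cellular and biopsy endpoints that leaves out samples taken after another vaccine.
4. In Section 2.2, state whether the plasmablast, activated B cell and biopsy counts are total or cholera-specific. This settles how much the point matters.

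The cost is one phrase in one criterion, one question at an existing visit, and a few sentences in Sections 2.2 and 7. Some subjects seen late would defer an elective vaccine by up to 14 more days. The change does not cover the Group 2 biopsy or the Day 90 and Day 365 blood draws, which also lie outside the bar.

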6.2.4 Visit 05a (EGD +7 days) and Visit 06a (EGD day+7 days)	20
6.2.5 Visit 07 Day 365	20
6.3 Early Termination Visit (if needed).....	20
7 Statistical Considerations	21
8 Quality Control and Quality Assurance.....	22
9 Ethics/Protection of Human Subjects	23

9.1 Ethical Standard	23
9.2 Institutional Review Board	23
9.3 Informed Consent Process	23
9.4 Exclusion of Women, Minorities, and Children (Special Populations)	24
9.5 Subject Confidentiality	24
9.6 Future Use of Stored Specimens.....	24
10 Literature References	25

SUPPLEMENTS/APPENDICES

A: Study Schedule.....	28
B: Adverse Events Grading.....	30

Protocol Summary

Title:	Immunologic Responses to a Live Attenuated Oral Cholera Vaccine
Population:	50 subjects, 18 to 49 years old, who are in good health and meet the eligibility criteria
Clinical Sites:	The Hope Clinic of the Emory Vaccine Center, Emory University Emory GI Clinic/Ambulatory Surgery Center
Study Duration:	5 years
Subject Duration:	Approximately 13 months
Description of Agent:	One dose delivered orally of the FDA-approved live attenuated cholera vaccine (Vaxchora)

Objectives:

Primary:

- To evaluate the antibody response to the cholera vaccine in healthy subjects.

Secondary:

- To evaluate B cell responses in healthy subjects receiving the live attenuated cholera vaccine.
- To evaluate the safety and reactogenicity in healthy subjects receiving the live attenuated cholera vaccine.

Exploratory:

- To evaluate mucosal cell responses in a subset of the healthy subjects receiving the live attenuated cholera vaccine.

Endpoints:

Primary:

- Level of antibody titers at day 1 (pre-vaccination) and day 29 in serum.

Secondary:

- Levels of plasmablasts at days 1, 8 and 29

- Levels of activated B cells at days 1, 8 and 29
- Levels of memory B cells at days 1 and 29.
- Correlation between antibody titers and the level of plasmablasts, activated B cells, and memory B cells.
- Production and characterization of monoclonal antibodies against *V. cholerae* at day 8 in a subset of subjects.
- Solicited and unsolicited adverse events in healthy subjects receiving cholera vaccine at day 8 and day 29 respectively.
- Serious adverse events in healthy subjects receiving cholera vaccine for the duration of the study.

Exploratory:

- Levels of plasma cells, activated B cells and T cells in small intestinal biopsy samples at day 29 (n=15) or day 90 (n=5).
- Correlation between systemic and mucosal immune responses.

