5.1.3 Specimen Collection, Preparation, Handling and Analyses

Blood will be collected at each of the seven study visits as per the Study Schedule in Appendix A.

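### Exclusion 10 states participation as 56 days, but it lasts about 13 months with blood draws to Day 365; read literally, donation plans from about Day 57 to the last draw are not screened for (minor wording error).

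*Combined protocol and SAP*

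**What the plan says.** Exclusion criterion 10 (Section 4.2) has three parts. The first excludes people who gave blood in the 56 days leading up to vaccination. The second excludes those who "plan to donate blood at any time during the 56-day duration of subject study participation". The third excludes those who "plan to donate blood within 56 days after the last blood draw".

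The rest of the protocol describes a much longer period:

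- The Protocol Summary gives subject duration as "Approximately 13 months".
- Section 3 says "Each subject will make a total of 7 visits to the Hope Clinic", and Section 5.1.3 adds "Blood will be collected at each of the seven study visits".
- Section 6.2 repeats "Blood will be collected for immunogenicity analysis" under the follow-up visits, including Day 90 and Day 365. Of Days 11 and 15 it says "Certain follow up visits (D11 and D15) will not be required by PI discretion".
- The blood collection row of the Appendix A schedule is marked at V06 (Day 90, window -4/+7) and V07 (Day 365, window ±14).
- Section 2.2 lists antibody titers at Days 90 and 365 as exploratory outcomes, so the late draws are planned study data.

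No other visible text deals with blood donation.

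**The concern.** The three parts appear meant to run on from one another: before vaccination, during the study, after the last draw. The 56-day figure breaks that sequence. It ends the middle part about ten months before the third part begins.

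Sections 4.1 and 5.0 have eligibility checked by history and interview, so in practice the criterion is a question put to the volunteer. Staff who ask about the stated 56 days would accept someone who plans to donate in month 3 or month 11, close to the Day 90 or Day 365 draw. Staff who read past the number would exclude the same person. What is at stake is consistent screening and a safeguard on blood loss. No estimate or test is affected.

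**Working it through.** **Inputs**

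- Length stated in exclusion 10: 56 days (Section 4.2).
- Subject duration: about 13 months (Protocol Summary).
- Screening window: Day -45 to Day -7 (Section 6.1.1).
- Draws at the numbered visits: Days 1, 8, 11 (optional), 15 (optional), 29, 90 and 365 (Section 6, Appendix A).
- Windows: Day 29 -7/+14; Day 90 -4/+7; Day 365 ±14 (Appendix A).

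**Can 56 days be reproduced?** No.

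- Day 1 to Day 365 is 365 - 1 = 364 days, or 350 to 378 with the window.
- Day -45 to Day 365 is 365 + 45 = 410 days. At 30.44 days per month that is 13.5 months, which agrees with the summary.
- Thirteen months is 13 × 30.44 = 396 days, and 56/396 = 14%.

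**Which draws fall after Day 56?** V05 is at the latest on Day 29 + 14 = 43. V06 is at the earliest on Day 90 - 4 = 86. Wherever visits fall in their windows, V06 and V07 come after Day 56. That is 2 of the 7 numbered visits with a draw, or 2 of 5 if V03 and V04 are not done. Appendix A also marks a draw at screening, which these counts leave out.

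**Length of the literal gap.** The criterion gives no start day. The gap runs from the day after the 56-day count ends to the day before the last draw.

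| Count starts | 56 days end | Gap, last draw Day 365 | Last draw Day 351 | Last draw Day 379 |
|---|---|---|---|---|
| Day 1 | Day 56 | 364 - 57 + 1 = 308 | 350 - 57 + 1 = 294 | 378 - 57 + 1 = 322 |
| Day -7 | Day 49 (7 + 49 = 56) | 364 - 50 + 1 = 315 | 301 | 329 |
| Day -45 | Day 11 (45 + 11 = 56) | 364 - 12 + 1 = 353 | 339 | 367 |

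The screening rows assume there is no Day 0; counting one adds a day to each. Treating the day of the last draw as uncovered also adds a day throughout. Day 1 is the literal start that gives the smallest gap.

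**How much of the gap is near a draw?** Apply the criterion's own 56-day margin to the nominal draw days, within Days 57 to 364:

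- Day 90: Days 57 to 146 (90 + 56 = 146), which is 90 days.
- Day 365: Days 309 to 364 (365 - 56 = 309), which is 56 days.
- Total: 90 + 56 = 146 days. The other 308 - 146 = 162 days (147 to 308) are more than 56 days from any draw.

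**If the phrase means all of participation,** the middle part runs to the last draw and the gap is 0.

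**The case against.** The strongest reply is that the intent is plain. The phrase refers to any time during participation, and the next part continues from the last draw. The figure 56 also stands in the parts on either side, so it may simply have been carried over. This is probably right, and it means the gap arises only on a literal reading. It does not make the number correct, and an eligibility rule should not depend on staff ignoring the figure it states.

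Second, the 308 days overstate the exposure, since only 146 of them lie within 56 days of a nominal draw. That stands as a limit on size. Those 146 days do include the approach to both late draws, which the criterion appears designed to protect.

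Third, harm is not shown. No draw volumes are given, recruitment is through one institution, and the consent pages are not in the material available, so a donation instruction there cannot be ruled out. All of this stands. An instruction in the consent form would reduce the practical effect but would leave the criterion wrong.

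Fourth, the protocol calculates nothing here, so this is an inconsistency of wording and the exact day counts depend on convention. That is fair. The counts show scale only.

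**Conclusion.** The point holds as a minor wording error. The conflict between 56 days and about 13 months is certain, because both figures stand in the current text and the schedule supports only the second.

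The screening gap is conditional. It is 308 days (294 to 322) if the 56 days are applied literally from Day 1, longer if counted from screening, and zero if the phrase is taken to mean all of participation. On the literal reading from Day 1, about 146 days of the gap matter by the criterion's own margin.

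The benefit of correction is participant protection and uniform screening, and the documents do not allow it to be quantified. The primary endpoint, the target of 50 subjects and the descriptive analysis are unaffected.

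**What to change.** In the middle part of exclusion 10, strike the modifier 56-day and add *(through the Day 365 visit)* at the end of that part. Leave the first and third parts as they are, and change the matching line on the eligibility form.

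The criterion would then bar donation continuously from 56 days before vaccination to 56 days after the last draw, nominally 56 + 365 + 56 = 477 days. If that was always the intent, nothing changes in practice. If sites have been applying 56 days, the eligible pool narrows to leave out people who plan to donate during the year, including those whose plans fall far from any draw. The documents give no donation rate, so the loss cannot be sized. Visits, endpoints, sample size and analysis do not change.
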